powered however for a 12-month comparison which it is anticipated would come from comparisons of collections made initially at 0 vs 12 months, but with additional comparisons (subject to study continuation) at 6 vs 18 months etc. We base calculations on a current base resistance marker frequency (the Cyp6 gene-cluster marker haplotype described above) of 0.72, which is based on recent local data we have obtained. A projected 5% annual decrease in the PBO arm and 5% increase in the standard LLIN arm, translates into a projected difference between arms of approximately 10% per year. The total number of *An. gambiae* required per collection period to detect such a difference as significant (using an exact test) is N=1392 (allowing a two-fold higher collections in standard-LLIN houses than PBO-LLIN houses). Clustering is not accounted for in the analysis because we postulate (based on general patterns for the species) that it is unlikely there will be significant *a priori* population genetic structure within the *An. gambiae* population of Sud Ubangi.

Allowing for 16% non-*An. gambiae* in collections (based on our data from neighbouring Nord Ubangi province; Lynd et al. 2018) equates to a total of 1,650 Anopheles per survey period. Allowing for an average catch of N=3 *An. gambiae* per standard-LLIN house, and 1.5 in PBO LLIN houses this would require a total number of N=734 houses to be sampled by prokopack collections during each collection around the 6 month periods. We will sample from 4 clusters per arm to reduce travel costs and time). Specifically, we will sample from 3 separate health zones per arm and then from both PBO- and standard-LLIN clusters within the mixed Boto health zone. Villages to be sampled will be those in close proximity to the health centres included in the epidemiological component of the study.

It is intended that the same houses would be sampled each time, though if this is not possible, or if verbal consent to access to sample is not provided a neighbouring replacement house would be recruited. The projected 10% decrease is annual and therefore the main comparisons would compare surveys separated by 12 months, i.e. months 0 vs 12, 6 vs 18, 12 vs 24, etc.

Secondary entomological outcomes

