The primary entomological outcome measure will be the frequency of the molecular deltamethrin resistance marker haplotype. A single species (An. gambiae) is predominant in the study area. Anopheles gambiae typically show limited genetic differentiation even over large spatial scales (Miles et al 2017) and it unlikely that initial marker frequencies will show spatial variation, as noted above. Therefore analysis is planned for an inter-arm comparison using an exact test procedure. However, we will also examine whether spatial autocorrelation is present and introduce a spatial component into analysis using a generalised linear model if this is the case. Other important entomological outcomes (below) include the abundance of mosquitoes. The first secondary entomological outcome – abundance of female malaria vector mosquitoes, which is likely to show much higher variance even at local scales will be analysed using a Poisson generalised linear model with negative binomial link function to determine whether a difference in the density per house between study arms is present annually (i.e. from two 6 monthly collections pooled). Similar analysis will be performed for a measure of the malaria transmission rate – the entomological inoculation rate, which is estimated as the mean number of sporozoiteinfected mosquitoes per house per night, adjusted for the number of sleepers per house (identified from household questionnaire data), again based on the two 6 monthly collections pooled.

Key secondary entomological indicators (all to be measured biannually from the same collections)

Abundance of female Anopheles malaria-vector mosquitoes

Counted from the prokopak collections. Power calculations from the study design above suggest that detection of an annual 50% decrease in *Anopheles* abundance can be detected with >80% power.

Blood feeding rate of female Anopheles malaria-vector mosquitoes

From assessment of the bloodfed status of the above mosquitoes, coupled with limited random molecular testing of mosquito blood meals to quantify the human bloodmeal index.

Sporozoite rate in female Anopheles malaria-vector mosquitoes

Assessed from the same mosquitoes using molecular analysis of the head and thoraces of the females to determine the proportion infective.

Entomological inoculation rate

The number of infective bites/person/night calculated from preceding parameters and the number of sleepers in the house (obtained from questionnaire)

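### The primary entomological outcome is sized and tested as if mosquitoes were independent, although nets are allocated by zone and only 4 clusters per arm are sampled

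*Protocol*

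**What the plan says.** The randomisation section of the protocol assigns net type to whole health zones, with Boto split between types. The entomological sample size section takes a base marker frequency "of 0.72, which is based on recent local data we have obtained" and assumes "A projected 5% annual decrease in the PBO arm and 5% increase in the standard LLIN arm". It states that the total catch of *An. gambiae* needed in each survey "to detect such a difference as significant (using an exact test) is N=1392". The split between arms is 2:1, which the protocol describes as "allowing a two-fold higher collections in standard-LLIN houses than PBO-LLIN houses". Sampling is from 4 clusters per arm: 3 zones in each arm plus one part of Boto in each arm.

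On clustering the same section says "Clustering is not accounted for in the analysis because we postulate (based on general patterns for the species) that it is unlikely" that there is significant genetic structure a priori. The entomological data analysis section repeats the argument for initial marker frequencies and concludes: "Therefore analysis is planned for an inter-arm comparison using an exact test procedure". It adds that spatial autocorrelation will be examined, and that the analysts will "introduce a spatial component into analysis using a generalised linear model if this is the case". On timing, the sample size section says: "The projected 10% decrease is annual and therefore the main comparisons would compare surveys separated by 12 months".

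For the antenatal clinic (ANC) prevalence outcome, the epidemiological data analysis section plans mixed models with a correction for a small number of clusters.

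**The concern.** A pooled exact test counts each mosquito as a separately randomised unit, but the randomised unit is the zone. The defence is that *An. gambiae* shows little genetic differentiation, so zones should start alike. That bears on month 0. The hypothesis requires marker frequencies to move apart within about a year under the nets used locally. If selection can separate the arms in that time, differences in net use, coverage, starting frequency or local selection can also separate zones within an arm. A pooled test then reads that variation as an effect of net type.

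The effect of each net type on resistance selection is the second key deliverable, and results are meant to inform donors' choice of net. The ANC outcome has 8 zones per arm and is protected by a small-cluster correction. This outcome has half as many clusters and no such protection.

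**Working it through.** **Inputs from the protocol.** Base frequency 0.72; 5% fall (PBO) and 5% rise (standard); N = 1392 at 2:1, so n₁ = 464 (PBO) and n₂ = 928 (standard); 4 clusters per arm, so 116 and 232 mosquitoes per cluster if split evenly.

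**Assumed.** Two-sided α of 0.05 and 80% power (given only for the ANC outcome, without sidedness). The between-zone SD, s, of marker frequency is not given and is varied from 0 to 5 points.

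**1. Reproducing N = 1392.** Read as relative changes, 0.72 × 0.95 = 0.684 and 0.72 × 1.05 = 0.756, a difference of 7.2 points. With r = 2 and p̄ = (0.684 + 2 × 0.756)/3 = 0.732,

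n₁ = [1.96·√((1 + 1/r)·p̄(1 − p̄)) + 0.84·√(p₁(1 − p₁) + p₂(1 − p₂)/r)]² / (p₂ − p₁)² = 452,

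or 1356 in total; with continuity correction, 473 + 946 = 1419. Simulated Fisher power at 464 vs 928 is 80%. So 1392 is an individual-level size with a design effect of 1, counting one observation per mosquito. Read as absolute points (0.67 vs 0.77), about 699 to 744 would suffice, which does not reproduce 1392.

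**2. Type I error of the pooled test, before any fallback.**

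SE assumed by the test: √[0.72 × 0.28 × (1/464 + 1/928)] = 0.0255.

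True SE: √[s²/4 + s²/4 + (0.2016 − s²)(1/464 + 1/928)].

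At s = 0.02 this is √(0.000200 + 0.000650) = 0.0292, so the error is 2[1 − Φ(1.96 × 0.0255/0.0292)] = 8.6%. For haplotypes, n₁ and n₂ are doubled.

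| Zone SD (points) | Per mosquito | Per haplotype |
|---|---|---|
| 0 | 5% | 5% |
| 1 | 5.9% | 6.8% |
| 2 | 8.6% | 12.3% |
| 3 | 13.1% | 20.4% |
| 5 | 25.0% | 37.2% |

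Simulating Fisher's test itself gives 5–6%, 8–9%, 12–13% and 23–25% per mosquito at SDs of 1, 2, 3 and 5 points, and about 6%, 12%, 20% and 37–38% per haplotype. The protocol does not say whether mosquitoes or haplotypes are counted.

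**3. Power of a cluster-level t-test (6 df).** The noncentrality is the difference divided by the true SE under the alternative: 0.072/0.0258 = 2.79, 0.072/0.0294 = 2.45 and 0.072/0.0333 = 2.16 at SDs of 0, 2 and 3 points.

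| Reading | SD 0 | SD 2 | SD 3 | Pooled test, no clustering |
|---|---|---|---|---|
| 0.684 vs 0.756, per mosquito | 65% | 54% | 44% | 80% |
| 0.684 vs 0.756, per haplotype | 90% | 74% | 58% | about 98% |
| 0.67 vs 0.77, per mosquito | 89% | 81% | 70% | about 97% |

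The fall to 65% at SD 0 is the price of 6 df, not of clustering.

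**4. The fallback.** The protocol names no test for autocorrelation, so a simple within-arm heterogeneity test on the 8 clusters was tried in its place. It detects SDs of 2, 3 and 5 points with 16%, 31% and 68% power per mosquito (28%, 55% and 88% per haplotype). If a positive result leads to a cluster-level t-test, overall type I error is about 7–10% across these SDs.

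**5. Boto.** The two Boto clusters share a zone. If their zone effect is fully shared, pooled error at SD 5 points falls from 25% to about 21% per mosquito. The 6 df above are therefore approximate.

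**The case against.** The strongest defence is biological. The plan gives a reason for expecting little structure, and if frequencies do not vary between zones the exact test holds its 5% level. No between-zone SD is given, so every inflated figure is conditional. This stands as a limit on the size of the problem. It does not rescue the design, because the reason covers starting frequencies only and is itself put forward as a postulate.

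The second defence is the autocorrelation check. It has some effect: on one plausible version, error is about 7–10%. A reader might infer that the plan as written runs a 25% or 37% false-positive rate. The documents do not support that, since those figures leave out the check. But the check is a data-dependent pre-test that names no cluster effect or small-sample correction and leaves N unchanged.

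A reader might also take the 0 vs 12 month wording to mean that each arm is tested against its own baseline, for which N would be far too small. The documents specify no such single-arm test: the endpoint is comparative and the analysis is between arms. Likewise, the fall in power depends on the effect reading. If 5% means absolute points, cluster-level power stays near 80% up to an SD of about 2 points, although that reading does not reproduce N.

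**Conclusion.** The concern holds in conditional form. The protocol fixes an analysis that ignores the unit of allocation and a sample size with no allowance for it, and its justification does not cover the time at which the outcome is measured. Any between-zone SD above zero pushes the pooled test above its nominal level. A 2- to 3-point SD, small beside the 7.2-point effect that reproduces N, gives about 8–13% per mosquito before the fallback. Power for an analysis that respects clusters is then about 54% to 44%, against the 80% implied.

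These figures rest on an assumed SD, an even split of the catch over clusters, two-sided α of 0.05, and approximate treatment of Boto. That the pooled test is invalid whatever the SD, a conclusion a reader might draw, does not follow: at SD 0 it is valid. The sentence that calls the projected 10% a decrease is a lesser wording fault. The PBO fall is 5%, and about 10% is the relative gap between arms (0.756/0.684 = 1.105).

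**What to change.** - Make the primary test a between-arm comparison at month 12 that always accounts for cluster: either a cluster-level analysis or a binomial mixed model with a zone random effect and a small-sample correction.
- Treat the two Boto parts as sharing a zone, and use month-0 cluster frequencies for adjustment where available.
- Do not let the autocorrelation check decide whether clustering is allowed for. It can stay as a descriptive analysis.
- Restate power for 4 clusters per arm over a stated range of between-zone SD. Say whether mosquitoes or haplotypes are counted and whether 5% is relative or absolute.
- Reword the projected 10% decrease as a between-arm difference.

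The cost is revised text and a less favourable stated power; no new collections are needed for this. Regaining 80% power is a separate decision. At the same catch per cluster and the 7.2-point effect, it would take about 7 clusters per arm at an SD of 2 points (intracluster correlation 0.002) and 9 at about 3.2 points (0.005), counting one observation per mosquito.

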For the secondary entomological outcome, the density of malaria vector mosquitoes per house, the number of houses to be sampled to provide similar power is much higher, owing to the very high variability expected between houses (based on data from Protopopoff et al. 2018). Therefore, we will pool collections from the 6th and 12th month collection periods (providing a total of N=1468 house collections) to provide adequate power for this analysis to detect a two-fold difference in female *Anopheles gambiae* abundance between study arms (assuming a standard LLIN density of N=3/house).

Power calculations for or other main secondary entomological variable, the entomological inoculation rate, are prone to even higher variance but based on figures from (Protopopoff et al. 2018), the same strategy of pooled assessment from the 6 and 12 month collections as for density assessment should permit detection of the fourfold difference they observed (based on a standard LLIN mean of 1 and coefficient of variation of 6 in each arm).

Logistics: The poor transport network places limitations on feasibility of entomological collections in all zones and we therefore will sample from 4 clusters per arm, choosing those within closer travel distances from Gemena. The collection method proposed is by timed prokopak aspiration (10 min/house), providing a standardised and relatively inexpensive methodology for collecting adult mosquitoes, which can be used for abundance monitoring and infection assessment. In a large study evaluating LLINs in Uganda, aspirator collections have been made in houses (Lynd et al. 2019). Each zone involved will have a collection kit (prokopak, solar charger, batteries, etc) which will be transferred in turn to each of the four collection locations, within each of which we estimate approximately 25 house collections will be required, assuming catch rates of 3/house/collection in standard

Prokopak collection in Tanzania; AIRS 2016

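### The 734 houses per entomological survey divide a count of all Anopheles by a catch rate labelled An. gambiae, so the 16% species allowance enters twice; the error is conservative and needs a stated unit, not a smaller survey

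*Protocol*

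**What the plan says.** The derivation stands in the protocol under Entomological, Primary, Sample size calculation and power. The base marker frequency is given as "of 0.72, which is based on recent local data we have obtained", and the effect as "A projected 5% annual decrease in the PBO arm and 5% increase in the standard LLIN arm". The An. gambiae total needed per collection period "is N=1392 (allowing a two-fold higher collections in standard-LLIN houses than PBO-LLIN houses".

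The next paragraph allows for 16% of the catch being other species, a share observed "in collections (based on our data from neighbouring Nord Ubangi province"; the protocol says that this "equates to a total of 1,650 Anopheles per survey period". The sentence after that gives the average catch as 3 An. gambiae "per standard-LLIN house, and 1.5 in PBO LLIN houses" and concludes that "this would require a total number of N=734 houses to be sampled".

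Two later places reuse these figures. Secondary entomological outcomes doubles 734 to 1,468 pooled house collections. It powers a two-fold difference in female An. gambiae abundance, "assuming a standard LLIN density of N=3/house". The Logistics paragraph repeats a catch of 3 per house for standard-net zones and half that for PBO zones, but names no species.

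**The concern.** The species allowance converts a number of An. gambiae into a number of Anopheles. Once that is done, the catch per house must also be in Anopheles. The protocol instead divides by a rate that it labels An. gambiae, which already leaves out the other species. The allowance is therefore applied a second time, and 734 does not follow from its inputs as labelled.

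A one-word slip could explain this: the rates may have been meant as all Anopheles. But the secondary section attaches the same 3 per house to An. gambiae abundance. The rate is thus tied to An. gambiae in two places, and no single unit makes both sections right.

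At stake is whether the stated house requirement for the primary marker outcome is correct. The same count sets the size of each six-monthly survey and, doubled, the basis for the density and entomological inoculation rate (EIR) power statements. The gap is 115 houses per survey on one reading, or a density assumption of 3 where about 2.5 belongs on the other.

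**Working it through.** **Inputs from the protocol.** 1,392 An. gambiae per survey; 16% other species; 1,650 Anopheles; catch of 3 (standard) and 1.5 (PBO) per house; 734 houses; 1,468 pooled collections; base frequency 0.72; 5% changes in opposite directions. **Assumed**, because the entomological section gives no value: two-sided alpha 0.05 and 80% power. The house arithmetic does not depend on these two.

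**1. The mosquito target.** Read as relative changes, 5% gives 0.72 × 0.95 = 0.684 and 0.72 × 1.05 = 0.756. A two-proportion calculation at 1:2 allocation gives a total of 1,356 without and 1,419 with continuity correction. Two-sided Fisher exact power at 464 and 928 (1,392 split 1:2) is 80.0%. The target is reproduced under these assumptions. Read as absolute points (0.67 vs 0.77), the same formula gives only 699 to 744, so the relative reading fits.

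**2. The species allowance.** 1,392/0.84 = 1,657, which the protocol rounds to 1,650.

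**3. The protocol's house count.** Mean catch with equal houses per arm: (3 + 1.5)/2 = 2.25. Then 1,650/2.25 = 733.3, rounded up to 734 (367 per arm). Other routes do not give it:
- unrounded allowance: 1,657/2.25 = 736.5;
- equal mosquito numbers per arm from 1,650: 825/3 + 825/1.5 = 275 + 550 = 825;
- equal mosquito numbers per arm from 1,392: 696/3 + 696/1.5 = 232 + 464 = 696.

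**4. The same step in like units.**
- An. gambiae over An. gambiae per house: 1,392/2.25 = 618.7, so 619 houses, or 620 with equal arms.
- Anopheles over Anopheles per house: 2.25/0.84 = 2.68, and 1,657/2.68 is about 619.

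The difference is 734 − 619 = 115 houses: 15.7% of 734, or 18.6% above 619.

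**5. What 734 houses deliver if the rates are An. gambiae.** 367 × 3 = 1,101 and 367 × 1.5 = 550.5, together 1,651.5 An. gambiae (1,651.5/0.84 = 1,966 Anopheles). Fisher exact power at 550 and 1,101 for 0.684 vs 0.756 is 86.5%, against 80.1% at 465 and 930 (620 houses). Neither figure allows for clustering.

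**6. What follows if the rates are all Anopheles.** 734 houses give 1,651.5 Anopheles, of which 1,651.5 × 0.84 = 1,387 are An. gambiae; this meets the target apart from the rounding in step 2. The An. gambiae density becomes 3 × 0.84 = 2.52 and 1.5 × 0.84 = 1.26 per house, still a two-fold difference.

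Effect on density power: the protocol gives no dispersion, so I assume a negative binomial with k from 0.05 to 1, 1,468/2 = 734 collections per arm and no clustering. The variance of the log ratio is (1/m0 + 1/m1 + 2/k)/734, where m0 and m1 are the two densities.
- k = 0.05, 3 vs 1.5: √(41.00/734) = 0.2363; 0.693/0.2363 = 2.93; power 83.5%.
- k = 0.05, 2.52 vs 1.26: √(41.19/734) = 0.2369; 0.693/0.2369 = 2.93; power 83.3%.
- k = 0.1: 98.4% and 98.3%.

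The change is at most about 0.2 percentage points. The 2/k term dominates, so the means hardly matter.

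**7. What a cut to 620 houses would do.** Pooled collections fall from 1,468 to 1,240, or 620 per arm.
- Density at k = 0.05, 3 vs 1.5: 83.5% falls to 76.9%.
- EIR, with the protocol's own mean of 1, coefficient of variation of 6 and four-fold difference (1 vs 0.25, SDs 6 and 1.5): the standard error is √(38.25/734) = 0.228, and power 91%. At 620 per arm it is √(38.25/620) = 0.248, and power 86%.

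**The case against.** The strongest reply is that the slip costs nothing. It over-collects for the marker outcome, and the excess of about 19% in mosquitoes is the only margin in a calculation that leaves out clustering; a design effect of about 1.19 would use it up. This stands as a reason to keep the larger survey. It does not make the derivation right: the protocol presents 734 as what its inputs require, not as a margin. Household loss is covered separately, by consenting about 30% more households (Household recruitment, Mosquito collections).

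A second reply is that An. gambiae was written where Anopheles was meant. That would rescue 734, and it fits Logistics, which names no species, and Data analysis, which describes the outcome as female malaria vectors. It does not fit the secondary power statement, which names An. gambiae and uses 3 per house. Some rewording is needed on either reading.

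A reader might infer that the surveys are oversized and that 115 houses each (up to 690 visits if all six possible occasions take place) can be saved. The documents do not support this. Secondary entomological outcomes says that density needs far more houses than the marker does, and pools two surveys for that reason. The Logistics budget of about 25 houses at each of four locations, if taken as four per cluster over eight clusters, comes to 800 houses, above 734 and well above 620.

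A reader might also infer that the density and EIR power statements are materially overstated. They are not on this account: moving the density from 3 to 2.52 changes density power by about 0.2 points at most, and the EIR statement has its own mean and coefficient of variation and does not use the catch rate.

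**Conclusion.** The inconsistency is real and can be checked from adjacent sentences. The stated 734 is reproduced only by dividing all Anopheles by An. gambiae per house; on the labelled rate the marker endpoint needs 619 houses (620 with equal arms). Severity is minor, because the error runs in the safe direction and changes no endpoint or conclusion.

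The house figures rest only on the protocol's own numbers and on equal houses per arm. The power figures of about 86% against 80% also rest on two-sided alpha 0.05 and relative 5% changes, before clustering. If the changes were absolute, power would be about 97% to 99% at either size. The finding that density power barely moves rests on an assumed negative binomial dispersion of 0.05 to 1.

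The point does not show that the survey is too large for all its purposes, nor that the secondary outcomes are underpowered.

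**What to change.** State in the entomological sample size section whether 3 and 1.5 per house are An. gambiae or all Anopheles, and use that unit throughout.

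- **If An. gambiae:** restate the marker requirement as 620 houses. Keep 734 per survey (1,468 pooled), with the explicit reason that the density and EIR outcomes need it. Correct the expected yield to about 1,650 An. gambiae and give the resulting power with its alpha and effect size.
- **If all Anopheles:** correct the species label, keep 734, and restate the An. gambiae density in Secondary entomological outcomes as about 2.5 per standard-net house (1.26 per PBO-net house).

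Name the species in the Logistics paragraph to match. Do not reduce the survey to 620 houses on this ground alone. The cost is a few corrected figures and labels, with no change to field work.

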There needs to be one mixed assignment zone (Boto), which will primarily be a non-PBO distribution (see Table). For reasons of study power (below) it is crucial to organise the distribution such that the net types cluster around health centres used for assessment, to ensure that the zone can be retained as a cluster for at least one and hopefully both LLIN types in the study. The number of available PBO LLINs represents just under 25% of the total net need for Boto. As a result of logistical considerations and also to reduce the potential for mosquito dispersal between clusters with different types of LLIN a distribution plan to a cluster of western aires de sante is proposed for Boto (Figure 7).

Figure 7. Map of Boto health zone showing the western areas of Bomele, Bombili, Bobandu and Bokozo proposed to receive PBO LLINs (blue); all other areas will received standard LLINs. ?-1,2 show uncertain boundary locations between zones

If projected LLIN needs for each of the four areas are accurate, this would leave 2,000 surplus PBO LLINs, which could be distributed as close as possible, i.e. preferably along borders of these aires de sante to expand the size of the PBO-LLIN cluster.

More generally the mixed distribution in Boto could provide an important template for future distributions to provinces where division into fewer zones would preclude a statistically-useful comparative study if LLINs of contrasting types were distributed solely at the zonal level. Whilst statistically a distribution fully randomized at the level of aires de sante would be powerful, this is logistically challenging, may lack visible mapped impact on a malaria data map. Grouping of aires de sante - in the way proposed for Boto - could provide a viable intermediate distribution plan to meet statistical requirements, and, in addition to relative logistical ease also has the advantage of reducing the impact of human, net and mosquito movements among net-type clusters.

Proposal hypotheses and endpoints

Epidemiological

Primary

Hypothesis: PBO LLIN distribution will result in a lower malaria prevalence than standard (non-PBO) LLINs as indicated by reduced prevalence in ANC1 visitors.

Endpoint: monthly malaria prevalence in ANC1 visitors measured using RDTs, with main assessment points at 6 monthly intervals and intermediate assessments quarterly.

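### The marker comparison samples adjoining PBO and standard areas of Boto as opposite arms, with no rule on distance to the other net type and no allowance for mosquito movement in N=1392

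*Protocol*

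**What the plan says.** The primary entomological hypothesis is that marker frequency will stay level or fall in PBO zones while rising in standard zones. The sample size section starts from a "resistance marker frequency (the Cyp6 gene-cluster marker haplotype described above) of 0.72". It then assumes "A projected 5% annual decrease in the PBO arm and 5% increase in the standard LLIN arm", giving a "projected difference between arms of approximately 10% per year". For each survey round, the mosquito total needed "to detect such a difference as significant (using an exact test) is N=1392". This figure supposes that standard-net houses yield twice the catch of PBO-net houses. The only inflation is for 16% of catches being other species. Clustering is left out because genetic structure is not expected beforehand. The entomological Data analysis section supports this by saying that the species "typically show limited genetic differentiation even over large spatial scales".

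Four clusters per arm are sampled: three separate health zones per arm, and then "from both PBO- and standard-LLIN clusters within the mixed Boto health zone". The Logistics paragraph favours clusters nearer Gemena. Villages are those close to the study health centres. No buffer or distance rule is given.

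The section on randomisation and the distribution plan gives PBO nets to four western health areas of Boto and standard nets to the rest. One reason for grouping those four areas is to "reduce the potential for mosquito dispersal between clusters with different types of LLIN". About 2,000 surplus PBO nets could go along their borders to enlarge the PBO cluster.

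**The concern.** The endpoint works only if the two arms' mosquito populations move apart over 12 months. Mosquitoes that cross between a PBO and a standard area carry marker alleles with them and pull the two frequencies together. The protocol recognises this movement when it lays out the nets in Boto, but not when it decides where to measure or how many mosquitoes it needs. The low genetic differentiation cited to justify ignoring clustering is also at least compatible with gene flow that would oppose divergence, and the protocol does not discuss that side of the argument.

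At stake is how a null result can be read. If the marker frequencies do not separate, the trial could not tell whether PBO nets leave selection unchanged or whether alleles moved between areas. This is a primary outcome and a listed deliverable. The same houses are meant to be revisited at each round, so the choice of villages made at the first collection persists.

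**Working it through.** **Inputs from the protocol.** Base frequency 0.72; change of 5% down (PBO) and 5% up (standard); total 1392; 2:1 standard to PBO, so 928 and 464 mosquitoes; four clusters per arm, one of them in Boto.

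**Assumed.** Two-sided alpha 0.05 and 80% power. These are stated for the epidemiological calculation but not for the marker.

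**1. Reproduce 1392.** Reading the changes as relative: 0.72 × 0.95 = 0.684 and 0.72 × 1.05 = 0.756, a difference of 7.2 points. With r = 2 and p̄ = (0.684 + 2 × 0.756)/3 = 0.732,

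n(PBO) = [1.960·√(1.5·p̄(1−p̄)) + 0.842·√(p₁(1−p₁) + p₂(1−p₂)/2)]² / (p₂−p₁)²
= (1.063 + 0.467)² / 0.072² ≈ 452, total 1356.

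With continuity correction it is 473, total 1419. The stated 1392 lies between the two. Simulated power of Fisher's exact test at 464 and 928 is 80.8%.

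Reading the changes as absolute (0.67 vs 0.77) gives totals of 699 or 744, which do not match. So 1392 corresponds to the full, undiluted 7.2-point contrast, with no margin for movement.

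**2. Power if only Boto is diluted.** Assume equal weight per cluster and a difference centred on 0.72. If Boto keeps a fraction s of its difference, the pooled difference is 7.2 × (0.75 + 0.25s). Power = Φ[(d − 1.960·SE₀)/SE₁], where SE₀ and SE₁ are the standard errors under no difference and under d.

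For d = 0.072: (0.072 − 1.960 × 0.02518)/0.02578 = 0.878, so power is 81%.

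| Boto keeps | Pooled difference | Power, mosquitoes (464/928) | Total for 80% power, mosquitoes | Power, independent haplotypes (928/1856) |
|---|---|---|---|---|
| all | 7.2 points | 81% | 1419 | 98% |
| half | 6.3 points | 70% | 1845 | 94% |
| none | 5.4 points | 57% | 2502 | 85% |

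Totals use the continuity correction. The last column counts two independent haplotypes per mosquito. The protocol does not say which unit the exact test uses.

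On the absolute reading (10 points, about 98% power with mosquitoes as the unit), complete loss in Boto leaves 7.5 points and 84%.

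**3. Power without Boto.** Dropping Boto and not replacing its mosquitoes leaves 348 and 696. At 7.2 points, power is 69% counting mosquitoes.

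**4. How much exchange would matter.** The protocol gives no rate, so this shows only the range. Use a symmetric two-area model with g generations a year and a fraction m exchanged per generation: D(t+1) = (D(t) + 7.2/g)(1 − 2m), D(0) = 0. With g = 12 (assumed):

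| m per generation | Difference at 12 months | Share kept |
|---|---|---|
| 0.1% | 7.11 points | 99% |
| 1% | 6.33 points | 88% |
| 5% | 3.87 points | 54% |
| 10% | 2.24 points | 31% |

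The effect runs from negligible to severe depending on an input the protocol does not supply.

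**The case against.** A reader might infer that the protocol assumes one freely mixing population and so contradicts its own hypothesis. It does not say that. It says that genetic structure beforehand and spatial variation in initial frequencies are unlikely. Those are statements about the starting state. Low differentiation does not fix the share of mosquitoes exchanged over the next 12 months, and at 0.1% per generation almost nothing is lost. So the direction of the bias stands, but no particular size does.

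A reader might also extend the dilution to all sampled clusters. The other three per arm are separate health zones, in a province of about 52,000 km² with 16 zones (about 3,250 km² each on average). Boto is the only adjacency between sampled clusters that the text establishes.

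Nor do the surplus nets along the borders make matters worse. They enlarge the PBO cluster, and grouping the four areas was itself meant to limit dispersal. But the two sides still adjoin, and nothing keeps collection villages away from the line between them.

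The planned check for spatial autocorrelation is a real safeguard against dependence, but it cannot restore a contrast that movement has diluted.

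Finally, the bias is conservative, Boto offers a contrast under shared local conditions, and the protocol values it as a template for mixed distributions. These are good reasons to keep Boto. They are not reasons to leave the distance to the other net type uncontrolled and unreported.

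**Conclusion.** The point holds in a limited form. Two adjoining areas with opposite net types supply one of four clusters in each arm, villages are chosen without regard to the boundary between them, and the sample size assumes the full contrast. Any exchange acts towards no difference.

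The power loss depends on three things the protocol leaves open: the rate of exchange, whether the 5% changes are relative or absolute, and whether mosquitoes or haplotypes are counted. Complete loss in Boto alone leaves about 57% power on the relative reading with mosquitoes as the unit, and about 85% with independent haplotypes. These figures ignore clustering, as the protocol does. They do not show that the endpoint will fail. They show that a null result would be hard to interpret unless distance to the other net type is controlled and reported. This is a cheap improvement, not a fatal flaw.

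**What to change.** In the entomological sample size section, before the first collection round:

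- Within the areas already chosen, and as far as mapped boundaries allow, select collection villages around study health centres that lie furthest from the opposite net type, above all in Boto.
- Pre-specify the marker comparison with and without Boto, and by each village's distance to the nearest area of the opposite net type. The GPS house list already collected for the distribution can supply the village locations.
- State that the projected difference between arms assumes no exchange between them.

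The numbers of houses and mosquitoes do not change. The costs are somewhat longer travel to some villages and lower precision in the analysis without Boto (about 69% power counting mosquitoes). The protocol notes that health-area boundaries are not always precisely mapped and that parts of the Boto map are uncertain, so distances there will be approximate. Replacing Boto with another zone is not required; it would be a logistical trade-off that the protocol does not settle.
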